Statistical analysis plan

Title of the study: Split-in-situ Resection With Radio-frequency Ablation Instead of Liver Partition on the First Stage (RALPPS) in Patients With Hilar and Intrahepatic Cholangiocarcinoma

Unic Protocol ID: MCNC 09/2017

Date: October 24, 2017

Statistical analysis

The propensity score matching (PSM) method was used to overcome heterogeneity of retrospectively collected data in compared groups. Nearestneighbor algorithm with 1:1 match ratio using a 0.2 caliper was applied. Matching for stage 1 included following factors: maximum total bilirubin level, duration of jaundice and acute cholangitis presence. PSM model for stage 2 enrolled FLR volume after portal vein occlusion (first stage). Continuous data presented as median values were compared using Mann Whitney U test before and after PSM. The Two-tailed Fisher's Exact test was used for comparing categorical variables before and after PSM. A p-value of less than 0.05 was considered statistically significant. SPSS version 23.0 (IBM SPSS, Inc., Chicago, IL) software package was applied for data analysis.

[name], PhD,
Head of the HepatoPancreatoBiliary
Surgery Department,
Moscow Clinical Scientific Center
[contact]
www.mknc.ru

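### After 1:1 matching, the SAP's independent-sample tests ignore the matching factors and yield no effect estimate with a confidence interval; they are conservative to a degree the documents do not fix

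*SAP*

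**What the plan says.** The SAP's statistical analysis section sets the matching rule: "Nearestneighbor algorithm with 1:1 match ratio using a 0.2 caliper was applied". The stage 1 score uses "maximum total bilirubin level, duration of jaundice and acute cholangitis presence". The stage 2 score uses FLR volume measured after stage 1. The scale of the caliper and whether matching is with replacement are not stated.

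The same two tests then serve the unmatched and the matched data. For continuous data it names the "Mann Whitney U test before and after PSM". For the rest: "The Two-tailed Fisher's Exact test was used for comparing categorical variables before and after PSM". The decision rule is "A p-value of less than 0.05 was considered statistically significant". The section names no adjusted model, no variance that allows for the matching, and no between-group difference with an interval.

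The Protocol makes the percentage rate of FLR hypertrophy the primary endpoint, so Mann-Whitney is its test. The Protocol's paragraph on patient numbers plans 10 RALPPS and 20 PVE patients first, then 30 per group if early results are favourable. That allows at most 10 pairs, later at most 30.

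**The concern.** Mann-Whitney and Fisher judge the observed difference against the spread expected between two unrelated samples. Matching makes the groups alike on bilirubin, jaundice duration and cholangitis. If these factors drive hypertrophy, part of that spread can no longer appear as a chance difference between the groups, but the test still allows for it. The result is a test stricter than 5% that detects less than the same patients could show.

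The primary endpoint rests on few pairs, and the three factors have already been collected, so leaving them out of the comparison wastes information. A p-value without an interval also says little in so small a series about how large a difference remains plausible.

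**Working it through.** **Figure to reproduce.** The documents contain only the nominal level of 0.05. They give no effect size, SD, power, expected number of pairs, or strength of association between the matching factors and hypertrophy.

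**Step 1: analytic size.** Let ρ be the outcome correlation between matched patients. The variance of the group difference shrinks by (1 − ρ) while the test's variance does not. The true two-sided size is then 2 × [1 − Φ(1.96/√(1 − ρ))].

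- ρ = 0: 5.0%
- ρ = 0.1: 1.96/0.949 = 2.07, giving 3.9%
- ρ = 0.2: 1.96/0.894 = 2.19, giving 2.8%
- ρ = 0.3: 1.96/0.837 = 2.34, giving 1.9%
- ρ = 0.4: 1.96/0.775 = 2.53, giving 1.1%

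A size of 1-3% therefore needs ρ of about 0.18 to 0.42.

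**Step 2: simulated size after the whole procedure.** Common steps: logistic propensity score on three covariates, greedy 1:1 matching, then Mann-Whitney at two-sided 0.05. Assumed, because the documents are silent: R², the covariate shift between groups, a caliper of 0.2 SD of the logit, and no replacement. Set A has three normal covariates each 0.3 SD apart (about 19 pairs from 30 v 30). Set B dichotomises one covariate for the score and uses total shifts of 0.5 and 1.0 SD. Set C has one binary covariate and normal or skewed outcomes.

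| R² | A, 30:30 | B, 30:30 | C, 30:30 | B, 10:20 |
|---|---|---|---|---|
| 0 | 4.7% | 4.7-5.3% | about 5% | 4.5% |
| 0.1 | 3.6% | 4.4-4.8% | 3-5% | 3.8-4.2% |
| 0.2 | – | 3.9-4.0% | – | 4.3-4.8% |
| 0.3 | 2.7-2.8% | – | 2-3% | – |
| 0.4 | – | 2.1-2.7% | – | 2.8-3.6% |
| 0.6 | 0.9-1.0% | 1.7-2.1% | 0.5-1% | 1.7% |

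Monte Carlo error in set B is about 0.5 point. At 30:30, regression on group and the matching factors in the matched set had a size of 4.2-5.0% in set A and 4.7-6.3% in set B.

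**Step 3: power at 30 v 30** (Mann-Whitney / signed-rank / adjusted).

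- Set A, 0.8 SD, R² 0.3: 68-70 / 71-74 / 80-82%. Set C, with rank-based adjustment: 65% for Mann-Whitney v 76% adjusted.
- Set A, 0.8 SD, R² 0.6: 78 / 85-87 / 97%.
- Set B, 0.7 SD, total shift 0.5 SD: R² 0.1, 57 / 56 / 61%; R² 0.4, 63 / 67 / 77%.

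**Step 4: power at 10 v 20.** About 6-7 pairs survive the caliper.

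- Set B, 1.0 SD, total shift 0.5 SD: R² 0, 38 / 34 / 35%; R² 0.1, 38 / 33 / 38%; R² 0.4, 44 / 45 / 52%.
- Set B, 1.0 SD, total shift 1.0 SD, R² 0: 34 / 28 / 30%.
- Set C, R² 0: 45% for Mann-Whitney v 46.6% adjusted. Over R² 0-0.3, signed-rank had 30-38% against 45-48% for Mann-Whitney.

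Adjustment is thus level with Mann-Whitney, or up to about 4 points behind, when the factors predict nothing. It is ahead when they predict well.

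**Step 5: limits of exact paired tests.** With 5 pairs the smallest two-sided signed-rank p is 2/2⁵ = 0.0625, so significance is out of reach. The smallest Mann-Whitney p is 2/252 = 0.008. Exact McNemar with 5 discordant pairs gives at best 0.0625, so it needs 6 (2/2⁶ = 0.031). In a simulation with an assumed latent within-pair correlation of 0.2 and event rates of 70% v 20%, Fisher v McNemar power was 26% v 9% with 7 pairs and 43% v 38% with 10.

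**The case against.** The best defence is that the planned tests err on the safe side. Statisticians disagree on whether propensity-matched samples must be analysed as pairs, and a conservative test creates no false claims. Nothing in the documents shows that the matching factors predict hypertrophy strongly. The Protocol's contraindications even exclude acute cholangitis and bilirubin above 50 μmol/L, which might narrow their range, although the SAP uses the maximum bilirubin, which may be historical. A regression on so few patients is also fragile: 7 pairs give 14 patients, and 14 − 5 = 9 residual degrees of freedom.

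Much of this stands. It rules out three stronger readings that a reader might infer:

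- **That the 5% test really runs at 1-3%.** This needs an R² that the documents do not supply. With weak predictors the size is near 4-5%.
- **That paired tests must replace the planned ones.** At the initial 10 v 20, signed-rank is generally no better than Mann-Whitney and often worse, and exact McNemar is weaker than Fisher in the cases tried.
- **That the morbidity comparisons are shown to be biased towards no difference.** Conservatism could act that way, but its size was not computed for Fisher's test, and at the initial numbers McNemar would make the problem worse.

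The objection does not remove the narrower point. The dispute about pairing does not bear on covariate adjustment, which needs no pairing and uses variables already in hand. The missing interval is a gap whichever view one takes on pairing.

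**Conclusion.** The point holds in a conditional form. The matched analysis ignores the matching factors and provides no effect estimate with an interval. The tests are conservative to the extent that those factors predict hypertrophy: true size is about 1-5% over an assumed R² of 0 to 0.6, and 1-3% only from R² of roughly 0.3-0.4 upwards. At 30 v 30, R² 0.3 and 0.8 SD, about 65-70% power compares with 76-82% after adjustment. At 10 v 20 the gain is real only if the factors predict well.

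All of this rests on assumed R², covariate shifts, caliper scale and matching without replacement. The choice of test does not inflate false positives, so this is a worthwhile improvement, not a flaw that invalidates the plan.

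**What to change.** 1. Make the main matched-set analysis of hypertrophy a regression on group plus maximum bilirubin, duration of jaundice and acute cholangitis. Report the adjusted difference with its 95% CI.
2. If the outcome is skewed, use ranks or a transformation. One option is log(1 + rate/100), which equals the log ratio of post- to pre-procedure FLR volume. Ranks supply a test only, so take the interval from the unranked or transformed model.
3. For continuous stage 2 outcomes such as blood loss, adjust for FLR volume after stage 1, which is the SAP's own matching factor there. Stage 1 treatment may affect that factor; whether to condition on it at all is a separate question.
4. Keep Mann-Whitney and Fisher, labelled as supporting analyses that do not account for the matching factors. Do not substitute signed-rank or exact McNemar at 10 v 20.
5. State the caliper scale and whether matching is with replacement, and report the number of pairs.

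The cost is SAP wording: no new data and standard software. The downside is a model assumption and few degrees of freedom at about 7 pairs, with a possible loss of a few points of power there if the factors turn out not to predict hypertrophy.
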